- Data collection will occur through accessing the patients' chart to obtain LATCH scores throughout the study. This will be done through computers and laptops that have been encrypted through UnityPoint Health and/or OSF St. Francis Medical Center- no personal laptops will be used.
- Paper documentation will be held in a LOCKED cabinet in the PI office and will be scanned into the chart after 2 weeks. Once it is scanned into the chart, the paper copy will be destroyed.
- 2. How will data be collected from source documents and incorporated into the research record (paper case report forms, eCRFs, patient diary, eDiary, patient monitoring device, etc.)
 - Data will only be pulled from EPIC and only the patients' LATCH score will be recorded.
- 3. Describe the methods of storage of data (i.e., electronic, hard copy, specimens, artifacts, etc.)
 - A secure database of those enrolled in the study, which arm of the study they are enrolled, and their de-identified number will be stored in REDCap or Qualtrics or similar database
 - Data collection will occur through accessing the patients' chart to obtain LATCH scores throughout the study. This will be done through computers and laptops that have been encrypted through UnityPoint Health and/or OSF St. Francis Medical Center no personal laptops will be used.
 - Paper documentation will be held in a LOCKED cabinet in the PI office and will be scanned into the chart after 2 weeks. Once it is scanned into the chart, the paper copy will be destroyed.
- 4. Describe where each method of data will be stored and how each method will be maintained in a
- secured manner (i.e., encryption, password protection, use of Qualtrics or REDCap, etc.)
 - A secure database of those enrolled in the study, which arm of the study they are enrolled, and their de-identified number will be stored in REDCap or Qualtrics or similar database
 - Paper documentation will be held in a LOCKED cabinet in the PI office and will be scanned into the chart after 2 weeks. Once it is scanned into the chart, the paper copy will be destroyed.
 - REDCap or Qualtrics or similar database will be used for data compilation. Members of the research team will have access
 - Statistician will have access to de-identified data.
- 5. Describe who will have access to each method of data and how each method of data will be transferred to any collaborators.

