 - The attendings providing care to the newborns all have newborn admitting privileges and would be expected to either provide emergent care immediately themselves or call for assistance.
 - UnityPoint Health Methodist and/or OSF St. Francis Medical Center has onsite 24/7 neonatology specialists as well.
- 3. Is the language explaining provisions for medical care in the consent document? $\hfill\squareNo$

⊠Yes

4. Will there be a data safety monitoring board (DSMB)/ Data Monitoring Committee (DMC) assigned to this study?

27

 \boxtimes No - If **NO**, skip to Question 5.

□ If **YES**, describe the DSMB/DMC structure and meeting plan (for example: how often they will meet) and how the findings will be reported back to the individual investigators and the IRBs.

5. Does the research protocol have a data and safety monitoring plan?

□ Not Applicable. All of the following criteria are met: research is minimal risk, does not involve physical or therapeutic intervention with subjects, subject trauma or distress is not an anticipated risk and the sponsor does not require a monitoring plan.

⊠No - If NO, please describe the methods to be used in this study to monitor the ongoing safety of the subjects (please refer to the paragraph below for information to be provided.)

□Yes - If YES, please describe the data safety monitoring plan in detail here:

Data and safety monitoring plan should contain the following: safety information (including serious adverse events) to be collected, methods for collecting information (e.g., case report forms, at study visits, by telephone calls), frequency of data collection, frequency of cumulative safety data reviews, responsibility for oversight and reporting of safety data, if applicable, statistical tests for analyzing the safety data to determine if harm is occurring when not using DSMB and, if applicable, conditions that trigger an immediate suspension of the Research.

- Built in to our protocol is a way for any practitioner who is involved in the direct patient care of any of our subjects to reach out to the research team to request documentation of the procedures performed. This would reveal if the subject was in the control or treatment arm.
- Any inquiry of this sort will be further investigated by the research team, including but not limited to:
 - o Inquiring about adverse reaction
 - o Determining if the participant was in the control or treatment arm

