 - Further investigation as deemed necessary if the participant was in the treatment arm
- Because there is a paucity of research in this area, all report adverse reactions will be taken seriously and investigated
- Hazard ratios will be assessed

6. Is this a multi-center trial?

□No

⊠Yes

7. Is your site the lead site or serving as the data coordinating center?

□No----NA

□Yes - If **YES**, describe the plan for managing and communicating the following information among the multi-center sites:

- Unanticipated problems involving risks to subjects or others-The PI is available 24/7 for discussion of any unanticipated outcomes. The PI is responsible for communicating all outcomes to the IRB.
- Interim results-Reported yearly as part of scholarly work.
- **Protocol modifications-**The PI sends out updates to the research team when any updates occur to the protocol. This has been clarified through meetings and emails with the research team.
- 8. Will you be applying for a Certificate of Confidentiality? $\boxtimes No$

28

□No - Certificate already in place.

□Yes - If YES, please include this information (as well as any exceptions — for example: mandatory reporting, threats of self-harm) in the consent document. When the IRB approves your research, submit a request for a Certificate of Confidentiality to the appropriate federal agency. After you receive the Certificate of Confidentiality, you must submit an Amendment to the IRB and receive IRB approval. Research subjects may only be enrolled after IRB approval of the Amendment and Certificate of Confidentiality.

9. Does anything you are going to do have any effect on fetal development?
 □Unknown
 ☑ No. This will be performed on newborns.

□Yes

If the answer is YES or UNKNOWN, briefly describe, including a statement in the consent form for a woman of child-bearing potential (if she is presently pregnant or should she become pregnant) describing the risks involved and indicating the safeguards you will employ.

10. To your knowledge, has this protocol been reviewed and subsequently disapproved by any IRB? $\hfill\square$ No

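### Safety item 5 writes further investigation of reported reactions for the treatment arm only, and promises hazard ratios for which the data plan provides no event or event date

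*Protocol*

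**What the plan says.** Section 16 of the protocol records that there is no data safety monitoring board (item 4) and no data and safety monitoring plan (item 5). Under item 5 it describes what will be done instead. A practitioner caring for an infant may ask the team for the procedure documentation. The item then says "Any inquiry of this sort will be further investigated by the research team, including but not limited to" three steps: asking about the adverse reaction, establishing the infant's arm, and "Further investigation as deemed necessary if the participant was in the treatment arm". The next bullet, which has no arm condition, says "all report adverse reactions will be taken seriously and investigated". The last bullet reads in full "Hazard ratios will be assessed".

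The form's instruction for this item asks for "if applicable, statistical tests for analyzing the safety data to determine if harm is occurring when not using DSMB", so a test was optional.

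On data, Section 14, item 2 says "Data will only be pulled from EPIC and only the patients"; the sentence goes on to say that it is their LATCH score that is recorded. Section 14, items 3 and 4 describe a database of enrolled infants, "which arm of the study they are enrolled, and their de-identified number will be stored in REDCap" or a similar system. Appendix A (Scoring and follow up) sets LATCH assessments at baseline, daily in hospital and at two outpatient visits, giving 4 to 5 data points per infant.

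**The concern.** Two statements in item 5 do not fit with the text around them.

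First, two sentences cover all reports, while the step between them carries an arm condition and comes after the arm has been established. A team that follows the list as written will look harder at treatment-arm reports, knowing the arm. Section 12, item 3c keeps identifiers so that adverse outcomes can be looked up by arm, so a comparison between arms is intended. The control infants are the comparator for deciding whether a reaction has anything to do with OMT.

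Second, a hazard ratio needs a defined event, the time at which it occurred and the time at risk. If the research data hold no reaction and no reaction date, the promised statistic has nothing to be computed from.

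With no monitoring board and no monitoring plan, item 5 carries most of the protocol's safety monitoring. What is at stake is whether the trial can give an even-handed account of reactions in the two arms.

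**Working it through.** The protocol states no figure for safety, so the check is mainly a comparison of texts.

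**Arm condition**

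| Place in Section 16, item 5 | Scope |
|---|---|
| Lead-in: "Any inquiry of this sort will be further investigated by the research team, including but not limited to" | Any inquiry, no arm condition, open-ended list |
| Step 1: ask about the reaction | No arm condition |
| Step 2: establish the arm | No arm condition |
| Step 3: "Further investigation as deemed necessary if the participant was in the treatment arm" | Treatment arm only |
| Next bullet: "all report adverse reactions will be taken seriously and investigated" | All reports, no arm condition |

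A report reaches the team before step 3, so the number of reports is not changed by that step. What may differ is what is later known about a report: its nature, severity and likely cause. To put a size on this one would need the share of control-arm reports that are taken further, and how far. The documents give neither, so no figure is offered.

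**Hazard ratio**

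| Needed | Provided for in the research data? |
|---|---|
| Event (a reaction) | No field is named. Section 14, item 2 records the LATCH score only; items 3 and 4 add enrolment, arm and study number |
| Date of the event | No field is named |
| Observation period | Partly: LATCH visits in Appendix A, tied to visits and not to a stated length of follow-up |

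In Section 13, item 2 the general date-elements box reads as unticked and date of birth as ticked. The form was machine-read, so the conclusion does not rest on this.

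**What a descriptive summary would look like**

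The arm size comes from Appendix A (Population Sample Size). The difference is 9.22 − 8.18 = 1.04, the pooled SD is √((0.92² + 1.60²)/2) = 1.305, and the standardised difference is 1.04/1.305 = 0.797. A two-sided t-test at 0.05 with 90% power needs 34.08, so 35 per arm and 70 in total. With 10% attrition, 70/0.9 = 77.8, so 78, or 39 per arm. The protocol's figures reproduce; they matter here only for the 39.

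With no reported reactions among 39 infants, the exact (Clopper-Pearson) 95% interval has lower limit 0 and upper limit 1 − 0.025^(1/39) = 1 − 0.9098 = 0.090, that is 0 to 9.0%.

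**The case against.** **On the arm condition.** The lead-in covers every inquiry, its list is open-ended, and the bullet that follows covers all reports. Control infants receive evaluation without corrective treatment, so an OMT-specific inquiry has a natural place only in the treatment arm. Section 16, item 7 also makes the principal investigator responsible for communicating all outcomes to the IRB, whatever the arm. This has force. A reader might infer that control-arm reports are ignored, and the text does not support that. But an open-ended list does not explain why one listed step carries an arm condition that the next bullet lacks. Control infants are also handled during the sham session, so a reaction can be reported there too.

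A reader might also cite "This would reveal if the subject was in the control or treatment arm" as showing that the team is unblinded by the inquiry. That sentence describes what a requesting practitioner learns. The research team delivers both treatment and sham, and Section 14, item 5 says it is not blinded. The ordering argument rests on step 2 of the list alone.

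**On the hazard ratio.** The statistic, the event definition and the time origin are commonly left to a statistical analysis plan, which is not at hand. The restriction to LATCH scores cannot be literally complete, since arm and study number are stored as well. Hospital and clinic records are declared sources in Section 13, item 1, and clinicians outside the team may hand paper notes to it. All of this is fair. But an analysis plan cannot supply event data that the protocol makes no provision to collect. The paper notes are scanned into the chart and destroyed, and nothing moves a reaction or its date into the research data.

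**Conclusion.** The point holds as a minor one, in two parts. Item 5 writes a deeper research follow-up for one known arm while saying that all reports are investigated. It also commits to hazard ratios for which no event-time data are planned.

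Two stronger readings of the second part are not supported. It would be wrong to say that no follow-up is planned: Appendix A sets a visit schedule, and what is missing is the reaction and its date. Nor can the hazard ratio be faulted for low power or poor precision, because the protocol states no reaction rate, no target hazard ratio and no power goal for safety. Any such figure would rest on invented inputs.

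The size of any bias from uneven follow-up cannot be estimated. The one interval given assumes 39 infants in an arm and no reported reactions. The LATCH comparison and the sample size of 78 are not affected.

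**What to change.** 1. Reconcile the item 5 bullets so that research inquiry into, and recording of, a reported reaction do not depend on arm. Leave clinical care and the immediate availability of procedure documentation (Appendix A, Documentation) as they are.
2. Add three fields to the research database: reported reaction (yes/no), date and a short description. Amend the sentence in Section 14, item 2 to match. If the general date box in Section 13, item 2 is indeed blank, bring it into line.
3. Replace the hazard-ratio sentence with, for example: The number and proportion of infants with at least one reported adverse reaction will be given for each assigned arm with an exact (Clopper-Pearson) 95% interval, as a descriptive summary.

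The cost is three fields, a few wording changes and slight extra recording, mainly for control-arm reports. Treatment, LATCH collection and sample size do not change.

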Conflict of Interest Disclosure Form (for each Authorized Study Personnel listed in Section 5 of this form)

□ Full Protocol (if applicable)

□ Any applicable advertising, **grant proposals**, etc.

Current CITI certifications and current CV for all those listed in section 5 of this form, if not already

submitted to the IRB.

□Any applicable questionnaires, surveys, data extraction sheets

Full Review:

⊠ Project/Protocol Review Form

⊠ Informed Consent, please be sure the footer includes a version date

Protocol Summary (must follow outline in section 6 of this form)

Responsibilities of Investigators Form

Conflict of Interest Disclosure Form (for each Authorized Study Personnel listed in Section 5 of this form)

⊠ Full Protocol

□Investigator's Brochure (if applicable)

Device Technical Manual (if applicable)

⊠Any applicable advertising, **grant proposals**, etc.

 \boxtimes Current CITI certifications and current CV for all those listed in section 5 of this form, if not already

submitted to the IRB.

⊠Any applicable questionnaires, surveys, data extraction sheet

31

Appendix A- Research Protocol

Objective: The objective of this project is to see if Osteopathic Manipulative Treatment (OMT) as an adjunct protocol to lactation support for infants with feeding dysfunction improves outcomes. Null hypothesis: Term newborns with feeding dysfunction do not improve with the addition of OMT compared to lactation support. Primary Question Alternative: In term newborns with feeding dysfunction, OMT added to lactation support will significantly improve feeding outcomes.

Background. Osteopathy, founded by Andrew [name], adds manual medicine, which stresses the importance of structure and function, to pre-existing medical philosophy and education. Doctors of Osteopathy (DOs) use Osteopathic Manipulative Treatment (OMT) to treat somatic, or bodywork, dysfunction which can include one or multiple body systems, such as muscular, skeletal, arthrodial, vascular, lymphatic, myofascial, connective tissue, or visceral (organ). Doctors of Osteopathy use OMT to treat somatic dysfunction which will improve structure and in turn, improve function. There are an array of techniques of therapy used by DO's, the type of treatment based on the diagnosed dysfunction, practioner comfort, and the needs/limitations of the patient.

Nipple feeding requires a complex set of actions to coordinate suck and swallow. There is a three phase process including oral, pharyngeal, and esophageal phases. Effective oral and pharyngeal phases depend on normal function of the intrinsic muscles of the tongue as well as the extrinsic stabilizing muscles. Normal feeding is also dependent upon action of the Vagus, Glossopharyngeal, and Hypoglossal Nerves and therefore normal anatomy of the jugular and hypoglossal foramen.

Research has shown there are common physiological dysfunctions/cranial strains associated with infant labor and delivery that may impair feeding function through abnormal structure affecting the muscles and/or nerves needed for normal suck and swallow function.

32

Past studies such as [name] 1998 pilot study on osteopathic treatment of infants with a suckling dysfunction have found OMT efficacious in conjunction to lactation support in infants with feeding dysfunction. Other studies on OMT in newborns have found the practice to be safe, cost effective, and shown to decrease length of stay.

Randomization: Newborns that are on the lactation rounding list and that meet criteria of our study will be given this brochure and offered admission into the study by the nurse or the lactation specialist caring for the newborn. If the parent is interested in participation in the study, the nurse or lactation specialist will put in a consult for the OMT team and page a member of the research team who will then consent the parent. The newborn will then be single blinded (to lactation) and randomized to either the treatment or control group. No new patients will be enrolled into the study on Fridays as our goal for all the newborns is to have at least *two* treatments before discharge and the OMT research team is only available Monday-Fridays. New enrollment will only occur Monday-Thursdays. Newborns that meet inclusion criteria will then be offered into the research study after obtaining informed consent from the parents. After listing all qualifying newborns alphabetically, newborns will be randomized into treatment/control groups in an alternating fashion.

Protocol for Control Group: Because OMT is a manual therapy, blinding to other participants in the study (lactation team and parents) would be difficult without a sham protocol occurring in the control group. As such, our protocol for the Control Group will be evaluation of cranial strain patterns and cervical motion. These findings will be evaluated, documented, but no corrective treatment will be delivered.

Protocol for Treatment Group: Each newborn in the treatment arm of our research group will receive the same OMT treatment protocol, regardless of somatic dysfunction. The benefits of using a protocol approach are: 1) All OMT providers can be trained and achieve comfort in the treatment options, 2) Eliminates the variable of different treatment options being more/less effective, 3) More accurate information regarding risks/benefits can be communicated to parents, 4) Minimizes inter-researcher outcomes.

The protocol was established by conducting interviews with OMT practitioners both locally and faculty at Osteopathic Medicine faculty at schools in different states. The finalized protocol is as follows:

Protocol:

- 1. Condylar Decompression
- 2. Still Technique to Cervical Region, including the Sternocleidomastoid Muscle
- 3. Balancing of the Hyoid Bone
- 4. Myofascial Release of Thoracic Inlet

Schedule: The OMT research team will conduct research Monday- Fridays. Newborns meeting criteria will be

34

enrolled on Monday-Thursdays. Treatment or sham treatment for the control group will take place Monday-Friday. The OMT research team will provide treatment and sham treatment to both inpatient and outpatient infants who are enrolled in the study. This will occur in the newborn nursery, patient room, or the lactation office. Residents and attending physicians will provide treatment and sham treatments, all residents will be directly supervised by an attending physician.

Documentation: It is important to blind the lactation team to which newborns receive treatment, as it is lactation who will assign the L.A.T.C.H. scores. In an effort to blind the study, the OMT research team will document in each study participants' chart (regardless of if they are control or treatment group) a Progress Note that read "This newborn is part of the Osteopathic Manipulative Treatment for the Management of Feeding Dysfunction in Breastfed Newborns Research Study. They may be in either the control or treatment group. Their documentation is available immediately by contacting the research team or by looking under Media tab in the next two weeks." This will allow someone to access the information immediately if needed due to any side effects but also allows for blinding of the lactation team.

Scoring and follow up: Infants in both control and treatment groups will have a L.A.T.C.H. assessment at baseline, daily during hospitalization, and at the first two outpatient lactation visits. The L.A.T.C.H. assessment will evaluate Latch, Audible swallow, Type of nipple (mother's nipple), and Hold. While OMT can affect most components of the L.A.T.C.H. assessment, it cannot affect the mother's type of nipple. Therefore, although the L.A.T.C.H. assessment will evaluate the nipple type, this data will not be used in our research. For research purposes the highest L.A.T.C.H. assessment score will be 8 (eight). We will collect baseline, daily assessments, and the two outpatient assessments which will result in 4-5 data points for each infant. These scores will be used to assess the benefit of the addition of OMT to the infants' care plan for feeding dysfunction.

Inclusion Criteria for Subjects.

- Term Infants greater than or equal to 37 weeks gestation
- Level I newborn
- Receiving lactation support
- Identified by lactation as having a newborn component to feeding dysfunction
- Admitted to UnityPoint Health Methodist hospital and/or OSF St. Francis Medical Center and available for follow up with Methodist lactation specialists and/or OSF St. Francis Medical Center lactation specialists.
- Available for at least 2 inpatient OMT sessions
- Informed Consent

Exclusion Criteria for Subjects.

- Infants <37 weeks of gestation
- Level II or III newborns
- Infants who are wards of the state
- Term infants who are receiving speech therapy or physical therapy
- Infants already receiving OMT

35

- Infants who are not breastfeeding
- Infants who have a feeding dysfunction mostly attributed to maternal factors (including but not limited to: abnormal nipples, maternal comorbidities, etc).
- Infants with Down's Syndrome or other contraindications for OMT(acute infection, fractures, etc.).

Population Sample Size:

- A. Estimated number of subjects: 78 (39 each
 - group)

A recent trial (Herzhaft-Le Roy 2016) has a significant improvement of LATCH score at the third day after intervention (mean=9.22, SD=0.92; mean=8.18, SD=1.60; p=0.001). Given the effect size, a power of 90% and a significance level of 0.05, a minimum total sample size of 70 is estimated. Considering an attrition rate of 10%, at least 78 (39 each group) subjects are needed for this trial.

- B. Age (inclusive) Term Infants greater than or
- equal to 37 weeks gestation.
- C. Sex (estimate M:F ratio) We estimate a 1:1 M:F ratio
- D. Describe the population from with which the sample will be drawn- please see above information.

Theoretical risks and potential benefits :

OMT is extremely safe and non-invasive. The OMT technique used per the protocol are gentle and indirect. No direct thrusting techniques will be employed. Investigators utilize minimal pressure during these techniques, so that there is no blanching of the investigator's nailbeds. However, as with any medical procedure, OMT carries some risk. Risks associated with the treatments to be used in this study include fatigue, headache, stiffness, tenderness, redness or mild swelling to the area after treatment. If treatment does not work, while patients do not appreciate any benefit they also do not usually show side effects. Patients who respond to treatment often begin feeling better within a day and then noticing improvement of their original symptoms (in this case, improved feeding). Potential benefits of treatment are improved feeding which includes improved latch of the baby, improved swallow, and reduced pain related to feeding for both mom and baby.

Alternative treatments to patients (if applicable).

No alternative treatments to OMT will be offered in addition to the lactation support already provided to breastfeeding infants and mothers who do not need a speech and/or physical therapy consult. Our OMT will augment the current standard for care which includes lactation support. Infants needing a speech and/or physical therapy consult in addition to lactation support will be excluded from the study.

Describe subject compensation, including plans for prorating.

Patients will not be billed for OMT. No monetary patient compensation will be offered

36

Version 3/12/2019 Amended previously on 9/6/2017 for assent of one parent, not two and contact info Created 6/7/2017 Comment [RJ1]: Paper is attached.

Comment [RJ2]: If you think there is a higher attrition rate, the sample size needs to be adjusted.

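### The arm-revealing record is scanned into the chart on a two-week clock not tied to the last LATCH score, so a later outpatient score is not protected from unblinding

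*Protocol*

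**What the plan says.** Appendix A, under Documentation, makes blinding of the scorers a requirement: "It is important to blind the lactation team to which newborns receive treatment". The stated reason is that these staff assign LATCH. Each infant's chart therefore carries the same neutral progress note in both arms, which ends: "Their documentation is available immediately by contacting the research team or by looking under Media tab in the next two weeks". The protocol says that this arrangement gives access in case of side effects and "also allows for blinding of the lactation team".

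Section 14 (Data Security Plan) gives the handling rule in items 1, 3 and 4: "Paper documentation will be held in a LOCKED cabinet in the PI office and will be scanned into the chart after 2 weeks". It continues: "Once it is scanned into the chart, the paper copy will be destroyed". Section 16, item 5, says that the documentation of the procedures performed shows whether the infant was in the control or the treatment arm.

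Under Scoring and follow up, Appendix A has LATCH assessed at baseline, on each hospital day and at two outpatient lactation visits, which makes 4-5 data points per infant. It gives no day, window or upper limit for the outpatient visits. The inclusion criteria place follow-up with the lactation specialists of the participating hospitals. By Section 14, research staff go to the "chart to obtain LATCH scores throughout the study", and item 2 adds: "Data will only be pulled from EPIC and only the patients' LATCH score will be recorded".

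**The concern.** The blind has an expiry set by elapsed time, while the scoring it protects ends with an event that has no date. Once the scan is made, the arm lies in the same electronic chart that holds the LATCH scores, and a note in that chart names the tab to open. Nothing in the protocol ties the scan to the last score, requires the outpatient visits to come first, or keeps lactation staff out of the scanned file.

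LATCH is an observer-assigned score and the only outcome score that Section 14 says will be recorded. If a scorer has seen the arm before an outpatient assessment, an effect of expectation on that score cannot be separated from an effect of OMT, and no later analysis can restore the blind. The sham procedure and the neutral note exist to prevent this. No scan date has to be recorded either, so scores taken after the scan could not be picked out afterwards.

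**Working it through.** No statistical calculation applies. The check sets the scan time against the scoring schedule.

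**Count of scores.** The plan gives 4-5 data points per infant, including 1 baseline and 2 outpatient scores. That leaves 4 - 1 - 2 = 1 to 5 - 1 - 2 = 2 daily inpatient scores, which is consistent with the schedule. The outpatient scores are 2 of the 4-5.

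**Scan time.** Let S be the day on which the two weeks start. On the Section 14 wording the scan falls at about S + 14 days. S is not defined. It could be enrolment, the first session, the last session or the date of each paper form. Under Schedule in Appendix A, sessions are given to inpatient and outpatient infants, so these readings can differ. A later S moves the scan later and narrows the gap; an earlier S widens it.

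**Comparison.** Let V1 and V2 be the two outpatient visits, with V1 before V2.

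- V2 before the scan: 0 scores follow the scan.
- V1 before the scan and V2 after it: 1 score follows the scan.
- V1 after the scan: 2 scores follow the scan.

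All three cases are compatible with the protocol, because V1 and V2 have no limit and S has no definition. These are counts of what is possible and carry no information on frequency.

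**The two statements of timing.** Section 14 puts the scan after 2 weeks. The chart note can be read as placing the record under the Media tab at some point within the two weeks. On that reading the gap opens earlier. The count above uses the later Section 14 timing, which is the more favourable to the plan, and counts no inpatient score as exposed.

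**Link to the design assumption.** The sample size rests on a published difference in LATCH at day 3 after the intervention, which lies inside the two weeks. A comparison at that time would not be exposed on the Section 14 wording. Appendix A nevertheless says that the collected scores, including the outpatient ones, will be used to assess the benefit of OMT. The planned numbers (70, raised to 78 for attrition) do not depend on this point.

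**The case against.** The strongest reply is that nothing has been shown to go wrong. For a score to be compromised, an outpatient visit must follow the scan, lactation staff must be able to open the Media tab, and a scorer must do so. The documents establish none of these. Early outpatient visits could all fall before the scan, and access to the tab is inferred only from the absence of a stated restriction. This stands, and it limits the point to an unprotected gap.

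A reader might infer that the outpatient scores are unblinded or biased. The protocol does not support that: neither the number of exposed scores nor any shift in scoring can be derived from it. A reader might also infer that the access provisions in Section 14, item 5, and Section 16, item 5, conflict or hand the arm to scorers. They do not. The first lists who may see which data, the second describes a safety enquiry, and neither names lactation staff.

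It can also be said that the two-week hold is itself a blinding measure, balanced against completing the newborn's chart. That is fair, but completing the chart does not require the scan to come before the last score. Finally, the Media tab is one of two routes to the record that the note offers for safety, so removing the pointer would reduce access. This objection stands, and the pointer should stay with its timing corrected.

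**Conclusion.** The point holds as a gap in the plan's own blinding rule. Section 14 releases an arm-revealing record into the chart by elapsed time from an undefined start, while Appendix A needs the lactation team blind until the second outpatient LATCH, which has no date. Up to 2 of the 4-5 scores per infant could be taken after the release. Exposure is zero if both visits precede the scan, and the documents do not show how often they would not.

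The conclusion rests on two readings: that the scanned paper is the documentation which Section 16 says reveals the arm, and that lactation staff can open the Media tab, since no restriction is stated. It is not a finding that unblinding would occur, and no size of bias is claimed. It should be fixed because the rule can defeat a blind that the protocol calls important, and the correction is a matter of wording.

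**What to change.** - In Section 14, items 1, 3 and 4, replace the two-week trigger. Scan the record only once the infant's second outpatient LATCH has been recorded, or by a latest date set by the sponsor for infants who do not return.
- Log the scan date for each infant, so that any LATCH scored later can be identified.
- In the chart note in Appendix A, reword the timing of the Media-tab pointer to match Section 14. Keep the pointer.
- Leave immediate access through the research team for safety as it is.

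**Cost.** The record reaches the chart later, and the paper stays longer in the existing locked cabinet. During the longer hold the research team remains the only route to the record, as it already is before the scan; Section 16, item 7, states that the principal investigator can be reached at all hours. Allocation is not at risk, because the study database holds "which arm of the study they are enrolled". An infant who returns after the latest date would still be scored with the record in the chart, but the logged date would show it. Sample size, sessions and visits do not change.
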